8.2. GENERAL METHODS

All statistical testing will be at the 5% level of significance (2-sided) and all point estimates for the comparison between treatment groups will be accompanied by 2-sided 95% confidence intervals. To preserve the Type 1 error a fixed sequence testing procedure will be adopted. Testing will be on the FAS. The order of testing for the primary and secondary endpoints will be:

1. Change from Baseline at Week 24 in distance walked during the 12MWT
2. Change from Baseline at Week 24 in the PROMIS T-score

Continuous variables will be summarized using the number of non-missing observations (n), mean, SD, median, minimum, and maximum. Categorical variables will be summarized using counts and percentages.

Unless otherwise specified, the estimated mean and median for a set of values should be displayed to 1 more decimal place than the original values, and SD should be displayed to 2 more decimal places than the original values. The minimum and maximum should be displayed to the same number of decimal places as the original values. Deviations from this convention may arise to take account of the relevance of the precision (e.g., the distance walked in the 12MWT is reported to the nearest cm, but there is no relevance in presenting the mean to the nearest mm). These deviations from convention will be documented in the relevant analysis sections below.

Percentages will be displayed with 1 decimal place; except percentages will not be presented when the count is zero and 100% will be presented as an integer. Unless stated otherwise, percentages of subjects will be based on the number of subjects with non-missing data in the analysis set used for the presentation.

Baseline will be taken as the last available non-missing assessment prior to study drug administration (Day 1). Although the time of completion is not collected for QoL questionnaires (MFIS, PGIS, PROMIS, SF-36, BPI or WPAI:SHP), any completed on Day 1 will be deemed suitable for baseline as the questionnaires are requested in the protocol to

be completed prior to dosing and, even if after dosing, there is no anticipated effect after a single dose.

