If the subject is still ambulatory, and therefore able to do the test, then consideration should be given to whether the subject is unwilling to perform the test, or prevented from (e.g., specialty clinic visit that prevents attending the study visit) performing the test due to reasons possibly related to PMM or study treatment. If the subject is still ambulatory but unwilling to perform the 12MWT, or prevented from doing the test, their distance will be imputed using a worst case imputation; unless the reason is unrelated to PMM or study treatment. The change from baseline distance will be imputed using a random draw from the normal distribution with a mean equal to the worst change from baseline reported over the study across both treatment groups, and the standard deviation for the raw changes from baseline at the relevant visit irrespective of treatment group. These values will only be determined from those assessments where subjects have walked for the full 12 minutes (i.e., those assessments where there were no intercurrent events). Twenty-five imputations will be made to match the multiple imputations mentioned below for missing data. The imputations will be restricted to ensure the value for the visit is ≥ 0 meters for the visit.

The same approach as detailed above in the previous paragraph, will be taken for subjects who discontinue study treatment and do not continue in the study; unless the reason for discontinuing from the study and withdrawing from the study are unrelated to their PMM or study treatment (e.g., site unable to continue having visits during pandemic). The special exception to this will be death; if a subject dies their 12MWD will be imputed as 0 meters.

If the subject attempts the 12MWT or 30STS test but stops the test prematurely due to reasons at least possibly related to their PMM their data recorded will be used in all analyses. Examples of reasons for incomplete tests which will be considered related to the subject's PMM include fatigue, weakness, tiredness, exhaustion or pain in limbs. In this situation it is assumed that the subject has walked as far as they could in the 12 minutes and the data is not regarded as missing.

An independent blinded adjudication committee will review the 12MWT cases. The structure, function and operation of the adjudication committee will be detailed in a separate charter.

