	Unable to perform the test for reasons possibly related to PMM or study treatment. Subject is not ambulatory at time of assessment.	0
	Unable to walk the full 12 minutes for reasons possibly related to PMM or study treatment*	Use 12MWD recorded
	Ambulatory subject unwilling to, or prevented from, performing the test for reasons possibly related to PMM or study treatment	Worst case multiple imputation
	Withdrawal from study for reasons possibly related to PMM or study treatment	Worst case multiple imputation
	Death	0
Missing Data	Unable to perform the test, or walk the full 12 minutes, for reasons unrelated to PMM or study treatment e.g., COVID-19	Multiple imputation (MAR cases)
	Unwilling to perform the test for reasons unrelated to PMM or study treatment	
	Withdrawal from study unrelated to PMM or study treatment	

* Note: This is the only adjudication decision where the distance walked for subject’s unable to walk the full 12 minutes is used in the analyses. For all other decisions the distance is set to missing prior to analyses.

Multiple Imputation

Missing values will be imputed with the SAS[®] MI procedure. Prior to imputation the missing data pattern will be assessed. To account for non-monotone missingness (i.e., for the 12MWT this would be where a subject has missing data for Week 12, but has data for Week 24), a Markov Chain Monte Carlo (MCMC) model will be used to impute the non-monotone missing data, followed by a sequential regression model to impute the remaining data. Randomization seed numbers will be specified for each part of the imputation to ensure consistency and repeatability.

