In the non-monotone procedure, means and variances from the available data will be used to determine the MCMC starting values; imputed values will be selected with maximum likelihood methods. Initially, 200 MCMC runs will be generated before selecting the first imputed data set. An additional 24 data sets will be generated to reflect the uncertainty due to missing values. The 25 datasets will be separated by 100 iterations of the MCMC. The number of datasets may be increased if the analyses are not found to be sufficiently stable with respect to p-values. Stability will be determined if the p-values are the same to the second decimal place after 3 repetitions. These imputations will be performed separately within each treatment group. The imputation model will include the same covariates as for the analysis model and the value at each scheduled time point. Thus, for the primary endpoint the model will include the stratification mutation factor (in the event of a mis-stratification, the actual value recorded on the database will be used) and the scheduled time points (Screening, Baseline, Week 12 and Week 24). Imputed values will be restricted to being plausible i.e., for the primary endpoint values will be restricted to ≥ 0 meters, and for the secondary endpoint PROMIS T-score will be restricted to ≥ 30.3 and ≤ 83.6 .

In the scenario where a subject has a missing baseline (either not collected or out of window) and the screening value is used as the baseline value, the multiple imputation model will preserve the time the data was collected. So in this scenario the screening value will be present and the baseline value will be missing and imputed. The imputed baseline values will only be used to facilitate the imputation of later visits and will not be used in the analyses. After imputation the imputed baseline values will be replaced with the observed screening value which will be used in the calculation of changes from baseline and analyses (e.g., as a covariate).

The resulting 25 datasets will then be passed through the sequential regression models to impute for monotone missing data. If the non-monotone procedure is not required 25 datasets will be generated from the monotone imputation.

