APPENDIX 1 – SAS® CODE

Primary Endpoint Analyses

1: Repeated measures mixed model analysis (MMRM).

```
proc mixed data=<dataset>;  
  class treatment(ref='Placebo') visit subject mutation(ref='Other');  
  model chg=mutation baseline treatment visit treatment*visit / ddfm=kr  
    solution;  
  repeated visit / subject=subject type=un group=treatment;  
  lsmeans treatment*visit / cl diff;  
  estimate 'REN001 - Placebo: W24' treatment 1 -1 trt*visit 0 1 0 -1/cl;  
  estimate 'REN001 - Placebo: W12' treatment 1 -1 trt*visit 1 0 -1 0/cl;  
run;
```

Assumptions:

- treatment is 2 levels e.g. 1=REN001; 2=Placebo
- visit is 2 levels e.g. 1=Week 12; 2=Week 24
- mutation is 2 levels e.g. 1=m.3243>G; 2=Other
- chg is change from baseline; baseline is baseline score
- An unstructured covariance matrix is specified using type=un. If this analysis fails to converge, then an ANCOVA approach will be used instead.

2: Non-monotone multiple imputation.

```
proc mi data=<dataset> seed=<seednumber> nimpute=25  
  out=<outmidataset1> minimum=(. 0 0 0 0);  
  by treatment;  
  var mutation scrn bl w12 w24;  
  mcmc impute=monotone chain=multiple nbiter=200 niter=100;  
run;
```

Assumptions:

- Dataset has one record per subject in a horizontal structure for observed values at each visit
- Observed values for endpoint at each visit are contained in the variables - scrn=screening, bl=baseline, w12=week 12, w24=week 24
- If a subject has a missing baseline (either not collected or out of window) then the screening value will be used as baseline. However, for the multiple imputation model the time the data was collected will be preserved so the *scrn* variable will be the screening value and the *bl* variable will be missing and imputed. The imputed baseline values will only be used to facilitate the imputation of later visits but will not be used in the analyses.
- mutation is 2 levels e.g. 1=m.3243>G; 2=Other
- treatment is 2 levels e.g. 1=REN001; 2=Placebo

3: Monotone multiple imputation.

```
proc mi data=<outmidataset1> seed=<seednumber> nimpute=1  
    out=<outmidataset2> minimum=(. 0 0 0 0);  
by treatment _imputation_;  
var mutation scrn bl w12 w24;  
monotone reg;  
run;
```

Assumptions:

- Dataset is the output dataset from the non-montone MI step, and already contains the 25 imputations for each subject denoted in the dataset by the variable `_imputation_`

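### Twenty-five imputations and an ambiguous two-decimal stability rule leave a borderline primary p-value dependent on the random seed

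*SAP*

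**What the plan says.** SAP 8.3.1 (Multiple Imputation) generates a first data set and then states "An additional 24 data sets will be generated to reflect the uncertainty due to missing values", making 25. The worst-case values for intercurrent events are also random draws, tied to the same number: "Twenty-five imputations will be made to match the multiple imputations mentioned below for missing data".

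On adequacy the SAP says "The number of datasets may be increased if the analyses are not found to be sufficiently stable with respect to p-values", and then "Stability will be determined if the p-values are the same to the second decimal place after 3 repetitions". It gives no increased number and no upper limit. It does not require the repetitions to agree on significance, and it does not say which repetition is reported.

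On seeds it says "Randomization seed numbers will be specified for each part of the imputation to ensure consistency and repeatability". No values or date are given, and the sample code in Appendix 1 carries a placeholder: "proc mi data=<dataset> seed=<seednumber> nimpute=25".

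SAP 8.2 sets the threshold, "All statistical testing will be at the 5% level of significance (2-sided", and the hierarchy, "To preserve the Type 1 error a fixed sequence testing procedure will be adopted". The 12MWT comes first and the PROMIS T-score second.

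**The concern.** The significance threshold lies in the middle of a two-decimal rounding bin. If agreement means equality after rounding, 0.046, 0.049 and 0.054 are all 0.05. Three repetitions can then be declared stable although two are significant and one is not. If agreement means equality after truncation, 0.049 and 0.051 differ and the rule works as a same-side check. The SAP leaves this open.

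The more general matter is simulation error. With 25 imputations the pooled p-value varies from seed to seed. Near 0.05 that variation can decide whether the primary test succeeds, and through the fixed sequence whether the only secondary endpoint is tested at all. SAP 2 places the analysis after unblinding, so unless seeds, number and reported run are fixed beforehand, they would be settled with treatment p-values in view.

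**Working it through.** **The plan's own figure.** SAP 3.5 states 93 per group for a 60 m difference, SD 125 m, two-sided 5%, 90% power. The standard error is 125 × √(2/93) = 18.33 m, so 60/18.33 = 3.273 and power is Φ(3.273 − 1.960) = 0.905 (0.9025 by the noncentral t). The figure is reproduced and is not in dispute.

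**The rounding window.** p = 0.045 corresponds to z = 2.005 and p = 0.055 to z = 1.919. At 93 per group that is an estimated difference of about 35.2 to 36.7 m (1.919 × 18.33 and 2.005 × 18.33). The chance that p lands in the window is 1.0% with no effect, 3.4% with a true effect of 36 m and 1.4% with 60 m.

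**Assumed input.** The documents give no between-imputation variance B or within-imputation variance W. I take B/W from 0.05 to 0.20, which is a fraction of missing information B/(W+B) of 4.8% to 16.7%. For scale, SAP 3.5 raises 186 to about 200, an allowance of 14, or 7 per arm of 100. If all 14 needed worst-case draws with SD 125 m, then B = 2 × 7 × 125²/100² = 21.9, W = 2 × 125²/100 = 312.5 and B/W = 0.07. The ratio would be lower once the shift to the worst change inflates W.

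**Model of one run with m imputations.** The pooled estimate is N(Q, B/m), and the estimated between-variance b is B·χ²(m−1)/(m−1). Total variance is T = W + (1 + 1/m)b, with Rubin degrees of freedom ν = (m−1)[1 + W/((1 + 1/m)b)]². The two-sided p comes from t with ν degrees of freedom. Q is set so that unlimited imputations would give the stated exact p. Three independent runs form a triple; each setting used 200,000 triples.

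At an exact p of 0.05 with m = 25, under rounding:

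| B/W | SD of p | triples that pass | of those, on both sides of 0.05 | straddling triples flagged as unstable |
|---|---|---|---|---|
| 0.05 | 0.005 | 28% | 72% | 73% |
| 0.10 | 0.008 | 14% | 62% | 89% |
| 0.20 | 0.012 | 7% | 45% | 96% |

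Hand check of the first SD: the SD of z is √(0.05/25/1.05) = 0.0436, and the slope of p at z = 1.96 is 2 × 0.0584 = 0.117, giving 0.0051. Variation in b adds a little.

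Under truncation 7% to 20% of triples pass and none straddles 0.05. The remaining 80% to 93% trigger the increase, for which no number is given.

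**Single run at an exact p of 0.048.** Chance of p ≥ 0.05:

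| B/W | m = 25 | m = 1000 |
|---|---|---|
| 0.05 | 37% | 1% |
| 0.10 | 42% | 5% |
| 0.20 | 46% | 12% |

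With m = 1000 the SD of p is 0.001 to 0.002.

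**Raising m but keeping the rule.** At an exact p of 0.05 with m = 1000, 99% to 100% of triples pass under rounding and 75% of those straddle 0.05. More imputations alone do not repair a rounding rule.

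**Check by full imputation of simulated data** (100 per arm, SD 125 m, assumed covariate R² of 0.5, p tuned near 0.05, m = 25, 900 seeds). With 12 of 200 missing, p ran from 0.036 to 0.063 (SD 0.0044), 36% of triples passed under rounding and 72% of those straddled 0.05. With 32 of 200 missing, p ran from 0.028 to 0.081 (SD 0.0078), 12% passed and 70% of those straddled. With few missing values the SD falls slightly below the range above.

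**The case against.** The strongest reply is that this is a narrow wording gap with safeguards around it, and much of that stands.

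- Truncation is a possible reading, and under it no straddling triple passes. A reader might infer that the SAP definitely accepts contradictory verdicts as stable. The text does not settle that.
- A reader might infer that the rule is useless near 0.05. At 25 imputations it flags 73% to 96% of straddling triples even under rounding. That protection is largely lost if the number is then raised.
- A reader might infer that the number of data sets could be tuned towards a favourable result. The trigger is disagreement between runs, not the direction of p, and the step adds simulation precision rather than patients.
- Seeds are already to be specified. Once fixed they make the result repeatable and, if fixed before unblinding, prevent choosing among runs. They do not make the verdict independent of the seed, and three repetitions need three seeds, one of which has to count.
- SAP 10.1.2 presents results for each imputation as well as pooled, so the Monte Carlo error of the estimate, √(B/m), could be calculated from planned output. It is not planned as a reported quantity.
- The event is rare. That limits the size of the concern, but a stability rule matters mainly for borderline results.

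**Conclusion.** The concern holds in limited form. The stability criterion is ambiguous, and under the rounding reading it can pass repetitions that disagree on significance. Under either reading, 25 imputations leave an SD of p of about 0.005 to 0.012 near 0.05, enough to reverse a borderline primary verdict. Seed values, their timing and the reported repetition are unspecified.

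The size rests on the assumed variance ratio of 0.05 to 0.20, and the pass and straddle rates apply only when the exact p is at 0.05. Overall exposure is small: p falls between 0.045 and 0.055 in about 1% to 3% of trials for true effects from 0 to 60 m. The documents do not support the stronger inference that the primary verdict generally hangs on the seed. The point still deserves correction, because the primary result gates the PROMIS test and the remedy is cheap.

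**What to change.** Before unblinding, amend SAP 8.3.1 and Appendix 1 to:

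- set one large fixed number of imputations, for example 1000, for both the MAR imputation and the worst-case draws;
- record the seed value for each imputation step and name that run as the reported result;
- replace the two-decimal stability rule and the open option to increase the number. If a repeat-run check is kept, base it on whether unrounded p-values fall on the same side of 0.05, and state what follows if they do not;
- report the Monte Carlo error of the pooled estimate and of the p-value.

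The figure of 1000 is a judgement. It reduces seed dependence without removing it: at an exact p of 0.048 a run would still miss significance 1% to 12% of the time under the assumed ratios. The cost is SAP wording and computer time. No data collection or trial conduct changes.

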8.3.2. Pharmacokinetic Data

Missing data will not be imputed.

Mavodelpar concentrations reported as below the limit of quantification (BLQ) will be taken as zero for linear plots, and equal to the LLOQ for log-linear plots. BLQ will be taken as zero for the computation of descriptive statistics.

8.3.3. Safety Data

AEs with missing classification should be queried prior to database lock. However, if there are missing classifications in the final data the following will be assumed:

- missing causality will be taken as treatment related
- missing severity will be taken as severe

Missing seriousness will not be imputed. Such cases will be discussed in the CSR.

Handling of missing dates/times for the start/stop of medications and adverse events are detailed in [Sections 9.4](#) and [12.1](#) respectively.

Laboratory values that are less than the LLOQ or greater than the upper limit of quantification (ULOQ) will be set to the LLOQ or ULOQ respectively, for the calculation of descriptive statistics.

There will be no imputation for missing DXA data.

8.4. VISIT WINDOWS

Data will be assigned to ‘analysis’ visits using windowing (see table below). If more than one assessment (including the early termination or unscheduled assessments) falls within the same defined window, the on-treatment assessment closest to the target day with non-missing data will be used for analysis. If the scheduled visit assessment is on-treatment and

within the analysis window, then this will be used irrespective of other unscheduled assessments within the analysis window. If two assessment dates are at the same distance from the target day, the latest on-treatment assessment with non-missing data will be used for analysis. Off-treatment assessments will only be assigned to a visit window in the absence of an on-treatment assessment within the analysis window.

Visit	Target Day	Protocol Visit Window	Analysis Window	Analysis Interval
Baseline	1	NA	$\leq 1^*$	NA
Week 2	14	± 3	8 - 20	13 (± 6)
Week 4	28	± 3	21 – 35 [^]	15 (± 7)
Week 12	84	± 7	63 -105	43 (± 21)
Week 18	126	± 7	106 - 146	41 (± 20)
Week 24	168	± 7	147 - 189	43 (± 21)

* Baseline values must be prior to dosing if time of assessment is recorded.

[^] For pedometer data the lower limit of the analysis window will be widened to allow for the fact that the diary opens 2 weeks prior to the target visit date (Day 14 – 35).

If an unscheduled or early termination visit is mapped to a scheduled visit, then the type of visit will be identified in the appropriate listing together with the visit that it has been mapped to.

Any summaries of screening visit data will always be based on the data collected at the scheduled screening visit. Consequently, if the subject does not have baseline data collected at the baseline visit then the screening data will be used for both the summary of the screening visit and the baseline visit.

Follow-up visits by design are after the last dose of study drug and should not be allocated to on-treatment visits.

Windowing will not be used for the DXA scan data as there is only one measurement post dose.

Data collected outside these windows will not be attributed to an analysis window and will only be listed; unless specified otherwise in [Section 10](#) and [Section 10](#). Any scheduled visit outside the window will be identified on the appropriate listing.

